### **6.1.3. Prior Cancer Therapy**

The number of prior systemic cancer therapy regimens will be summarized for all subjects in the FAS. The component drugs of prior systemic therapy regimens will be coded using the WHO Drug Dictionary. The number and percentage of subjects with each drug will be summarized by WHO drug class and WHO drug preferred term. Regimen name, component drugs, start and stop dates, purpose of the regimen, best response, reason for discontinuation, and date of relapse/progression will be listed.

The number of subjects who received prior radiation will be summarized for the FAS. Radiotherapy type, location of administration, start and stop dates, reason for regimen, total dose, and best response will be listed.

The number of subjects who had prior surgery or surgical procedure for cancer treatment will be summarized for the FAS. Date and description of the surgery/procedure will be listed.

The number of subjects who had hematopoietic stem cell transplant (for hematologic tumor types as applicable) will be summarized for the FAS. Date of transplant, type of transplant, source cell, line of therapy, best response, date of relapse/progression, and the regimen and drug names used with the transplant will be listed.

### **6.1.4. Medical History**

Medical history will be coded to SOC and PT using MedDRA coding dictionary. For subjects in the FAS, medical history will be summarized by SOC and PT and listed.

## **6.2. Disposition of Subjects**

The number and percentage of subjects who were treated, discontinued study treatment with a primary reason for discontinuation, and withdrew from the study with a primary reason for withdrawal will be summarized and listed for the FAS.

The number of subjects enrolled by country and site will also be provided for the full analysis set.

## **6.3. Protocol Deviations**

Protocol deviations recorded on the eCRF will be summarized and listed for the full analysis set.

## **6.4. Exposure**

For subjects in the safety population, exposure to INCB059872, ATRA, azacitidine, and nivolumab will be summarized descriptively as the following:

### **6.4.1. Exposure for INCB059872**

- **Duration of treatment (days):** Date of last dose of INCB059872 – date of first dose of INCB059872 + 1.
- **Average reported daily dose of INCB059872 (mg/day):** Total reported INCB059872 dose (mg) / duration of treatment with INCB059872 (days).
- **Dose modifications for INCB059872:** Number of subjects who had INCB059872 dose reduction and interruption will be summarized.

#### 6.4.2. Exposure for All-Trans Retinoic Acid

- **Duration of treatment (days):** Date of last dose of ATRA – date of first dose of ATRA + 1.
- **Average reported daily dose of ATRA (mg/day):** Total reported ATRA dose (mg) / duration of treatment with ATRA (days).
- **Dose modifications for ATRA:** Number of subjects who had ATRA dose reduction and interruption will be summarized.

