## **5. TREATMENT**

INCB059872 will be self-administered orally QOD or QD on a 28-day cycle. In each cycle of the QOD dosing schedule, subjects should receive 14 doses of INCB059872. In each cycle of the QD dosing schedule, subjects should receive 28 doses of INCB059872. Tablets will be available in 1 mg strength. The initial starting dose for Part 1 will be 2 mg QOD. The initial starting dose for other parts of the study will be based on the aggregate data review of Part 1.

For QOD administration, if a dose is missed by more than 24 hours, the subject should skip the dose and take the next scheduled dose at the usual time. For QD administration, if a dose is missed by more than 4 hours, the subject should skip the dose and take the next scheduled dose at the usual time. INCB059872 tablets should be taken on an empty stomach if possible (refrain from food consumption during the period 2 hours before and 1 hour after taking INCB059872). For subjects participating in the food-effect portion of the study in Part 2, TG B1, a high-fat, high-calorie meal will be consumed within 30 minutes before taking INCB059872 on Cycle 2 Day 1.

Alternative dosing regimens (ie, QD) may be explored based on emerging PK/█ and safety data.

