### **5.2.2.1. Tretinoin Capsules**

In Parts 3 and 4 TG C and TG C1, Tretinoin (ATRA) capsules will be administered as an open-label commercial product in accordance with local prescribing information at a dose of 45 mg/m^2 per day. The daily dose should be administered as 2 evenly divided doses. Drug is available in 10 mg capsules and should be stored in accordance with the package insert. Toxicity associated with tretinoin capsules will be managed per instruction in the package insert.

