#### **4.2.2. Body Surface Area**

For subjects in TGs C and C1 and TGs D and D1 (Parts 3 and 4), the BSA will be calculated based on the Mosteller ([1987](#)) formula as follows:

$$\text{BSA (m}^2\text{)} = \{[\text{weight (kg)} \times \text{height (cm)}] / 3600\}^{1/2}$$

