### **6.1. Baseline and Demographics, Physical Characteristics, and Disease History**

#### **6.1.1. Demographics and Baseline Characteristics**

The following demographics will be summarized for the FAS: age, sex, race, ethnicity, weight, height, BMI, and BSA (TGs C/C1 and TGs D/D1). Size of spleen and liver by manual palpation (for subjects with MF as applicable), and ECOG performance status at baseline will be summarized and listed for the FAS.

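### ATRA is assigned per m² but summarised only in mg/day, and the SAP defines no ATRA compliance, so no planned summary shows whether the assigned ATRA dose was delivered

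*SAP*

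**What the plan says.** **ATRA.** Protocol 5.2.2.1 sets the dose by body surface area: "45 mg/m 2 per day. The daily dose should be administered as 2 evenly divided doses". The same section says that the drug comes as 10 mg capsules. SAP 6.4.2 plans three summaries: duration of treatment, the average daily dose in mg/day, defined as "Total reported ATRA dose (mg) / duration of treatment with ATRA (days", and counts of subjects with reductions or interruptions.

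BSA is available for these subjects. SAP 4.2.2 states: "For subjects in TGs C and C1 and TGs D and D1 (Parts 3 and 4), the BSA will be calculated". It is then summarised at baseline (SAP 6.1.1: "weight, height, BMI, and BSA (TGs C/C1 and TGs D/D1") but does not enter SAP 6.4.2. SAP 6.4.3 gives azacitidine a BSA-adjusted relative dose intensity, and SAP 6.4.4 gives nivolumab a weight-adjusted one.

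Protocol 5.3.2 says that the sponsor will calculate ATRA compliance from drug accountability. SAP 6.5 defines compliance for INCB059872 only, and SAP 11.1 records no changes to protocol-defined analyses.

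**INCB059872.** SAP 6.4.1 defines duration as "Date of last dose of INCB059872 – date of first dose of INCB059872 + 1" and the average daily dose as "Total reported INCB059872 dose (mg) / duration of treatment with INCB059872 (days". Under QOD dosing, Protocol 5 expects 14 doses per 28-day cycle ("In each cycle of the QOD dosing schedule, subjects should receive 14 doses of INCB059872").

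**The concern.** ATRA is the only agent dosed by body size that has no size-adjusted exposure measure. Two subjects who take every capsule can have clearly different mg/day averages, and two subjects with the same average can have received quite different fractions of the assigned dose.

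Group C is a combination tolerability group, and Protocol 5.4.2 allows ATRA dose reductions, so a reader of its safety and response tables will want to know how much of the assigned ATRA was given. Escalation cohorts hold about 3 to 6 subjects per dose level (SAP 3.3). In rows that small, a chance difference in body size can look like a difference in ATRA delivery.

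The INCB059872 issue is smaller. The duration stops at the last dose and so leaves out the off-day that belongs to the last QOD dose. This pushes the QOD average upward and leaves the QD average unaffected.

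**Working it through.** The documents give no numerical result for these measures, so there is no figure to reproduce. The SAP formulas are applied directly.

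**ATRA**

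Inputs: assigned dose 45 mg/m²/day (Protocol 5.2.2.1). BSA of 1.5, 1.8 and 2.2 m² and a reported average of 80 mg/day are assumptions for illustration, since the documents give no BSA distribution.

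Formulas: full dosing in mg/day = 45 × BSA; percentage of assigned = 100 × 80 / (45 × BSA).

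| BSA (m², assumed) | Full dosing (mg/day) | 80 mg/day as mg/m²/day | Percentage of assigned |
|---|---|---|---|
| 1.5 | 45 × 1.5 = 67.5 | 80 / 1.5 = 53.3 | 118.5% |
| 1.8 | 45 × 1.8 = 81.0 | 80 / 1.8 = 44.4 | 98.8% |
| 2.2 | 45 × 2.2 = 99.0 | 80 / 2.2 = 36.4 | 80.8% |

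The same reported average is above, close to, or well below the assigned dose, depending on body size alone.

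Capsule rounding: with 10 mg capsules in two equal doses, whole-capsule daily totals move in steps of 20 mg. At 1.5 m² the neighbouring totals are 60 mg (60 / 67.5 = 89%) and 80 mg (119%). A size-adjusted measure would therefore carry some rounding for individual subjects.

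**INCB059872 under QOD dosing**

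A fully compliant subject taking n doses of d mg has total dose nd and a SAP duration of 2n − 1 days. The SAP average is nd/(2n − 1), the nominal value is d/2, and the ratio is 2n/(2n − 1).

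| Doses n | SAP average at 3 mg QOD (nominal 1.5 mg/day) | Overstatement |
|---|---|---|
| 1 | 3 / 1 = 3.000 | 100% |
| 3 | 9 / 5 = 1.800 | 20% |
| 7 | 21 / 13 = 1.615 | 7.7% |
| 14 (one cycle) | 42 / 27 = 1.556 | 3.7% |
| 28 (two cycles) | 84 / 55 = 1.527 | 1.8% |
| 84 (six cycles, about six months) | 252 / 167 = 1.509 | 0.6% |

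The percentages are the same at 2 and 4 mg QOD. For QD dosing, 28 doses of 4 mg over 28 days give exactly 4 mg/day, so there is no bias. Counting the last interval (2n days) returns d/2 for every n.

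The QOD average still registers missed doses. With 11 of 14 doses taken and the last on Day 27, it is 33 / 27 = 1.222 mg/day, or 81% of nominal, against 33 / 28 = 1.179, or 79%, with the full interval.

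**The case against.** The strongest reply is that this is a choice of unit in a descriptive table. BSA is summarised at baseline, ATRA reductions and interruptions are counted, and Appendix A of the SAP lists drug administration and demographics by subject. A reader could compare mean mg/day with 45 × mean BSA, or work through the listings. That stands to the extent that no data are missing. It does not supply the measure, because two separate group summaries cannot show how many subjects fell short. The reply also leaves the compliance gap open: Appendix A plans an exposure and compliance table, but the only compliance that the SAP defines is for INCB059872.

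A second reply is that capsule rounding would distort a relative dose intensity too. That is fair for individual values and needs a note. Rounding is bounded and can be explained, whereas mg/day mixes it with body size.

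Three stronger readings are tempting, and the documents do not support them.

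- **That the INCB059872 average is equally uninformative.** It is a flat mg dose, SAP 5.2 tabulates by initially assigned regimen, and SAP 6.5 adds percentage compliance (against the prescribed dose after modifications). The bias is a known factor of 3.7% or less from one full cycle on. Only subjects who stop within a few QOD doses, and overall rows that pool regimens, are materially affected.
- **That either average can look high or low under perfect dosing.** For QOD the error is always upward.
- **That dose selection depends on these averages.** Under Protocol 4.1.1, escalation and the MTD rest on DLTs, and the recommended dose rests on aggregate review of safety, PK and efficacy. Evaluability counts doses taken. Protocol 1.6.2 and 4.1.2 already state the monotherapy doses. Nor does any visible analysis relate Group C outcomes to ATRA exposure.

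**Conclusion.** The ATRA point holds. The readable SAP defines no summary that shows delivery of 45 mg/m² per day, and it gives no derivation for the compliance that Protocol 5.3.2 says will be calculated. Over the assumed BSA range of 1.5 to 2.2 m², an illustrative 80 mg/day stands for anything from 119% to 81% of assigned. A narrower BSA range would shrink that spread but not remove it.

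The QOD point is arithmetically correct but minor: 3.7% after one cycle, about 0.6% at the expected six months, and large only for very early stoppers. These sizes assume full compliance.

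Both points are improvements to descriptive exposure tables. No primary endpoint, dose decision or stopping rule changes.

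**What to change.** 1. **SAP 6.4.2.** Report the average ATRA dose in mg/m²/day using the BSA from SAP 4.2.2, and say whether baseline or most recent BSA is used. Add relative dose intensity = 100 × average (mg/m²/day) / 45. Note that rounding to 10 mg capsules moves individual values.
2. **SAP 6.5.** Add a derivation for ATRA compliance from drug accountability, as Protocol 5.3.2 foresees.
3. **SAP 6.4.1 (minor).** For subjects on QOD dosing at their last dose, use last − first + 2 days in the denominator of the average dose only, and leave the reported duration as it is. Restrict this to observed last-dose dates. SAP 4.1.4 imputes missing ones to the earlier of month end and treatment discontinuation, or to the discontinuation date, so an added day could overcount.

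The cost is a few lines in the SAP and a little extra programming. The inputs are already collected or derived, and no clinical rule is touched.

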#### 6.4.3. Exposure for Azacitidine

- **Number of cycles:** Number of cycles with a nonzero dose of azacitidine.
- **Relative dose intensity of azacitidine (%):**  $100 \times [\text{total actual dose}] / [\text{total assigned dose}]$ .

Total actual dose ( $\text{mg}/\text{m}^2$ ) administered is the sum of the BSA-adjusted cumulative dose of azacitidine that has been administered to the subject.

Total assigned dose ( $\text{mg}/\text{m}^2$ ) is the total dose expected if the subject had taken all doses as initially assigned. Let  $S$  be the study day of the last date that the subject is exposed to azacitidine. Let  $D$  be the assigned dose level of 75 in  $\text{mg}/\text{m}^2$ . The total assigned dose is defined as

$$\text{total assigned dose } (\text{mg}/\text{m}^2) = D \times 7 \times \lfloor S/28 \rfloor + \min[(S - 28 \times \lfloor S/28 \rfloor)/7, 1],$$

where  $\lfloor . \rfloor$  assigns the largest integer not greater than the argument.

- **Azacitidine dose modifications:** Number of subjects who had azacitidine dose reduction and interruption will be summarized.

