#### **4.1.5. Cycle Length and Duration**

Azacitidine will be administered as an open-label commercial product at a starting dose of 75 mg/m^2 subcutaneously or intravenously for 7 days during the first 9-day or less period (ie, a 2-day break allowed on weekend, if needed) of each 28-day treatment cycle. Nivolumab will be administered at a dose of 3 mg/kg as an intravenous infusion over 60 minutes every 2 weeks (Day 1 and Day 15 of each 28-day treatment cycle).

For combination therapy (Parts 3 and 4), Cycle 1 Day 1 is the day that the first dose of INCB059872, ATRA, azacitidine, or nivolumab is administered. Actual Day 1 of subsequent cycles will correspond with the first day of administration of azacitidine or nivolumab in that cycle; thus, treatment cycles may become out of sync with the originally planned schedule and cycle length may be different from 28 days. The date of Day 1 of subsequent cycles recorded on the eCRF will be used as Day 1 of the subsequent cycles.

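### The SAP's total assigned azacitidine dose leaves the last course unmultiplied by 7 × D, so a fully dosed subject shows a relative dose intensity of 52,500% after one cycle and about 200% after two

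*SAP*

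**What the plan says.** SAP section 6.4.3 (Exposure for Azacitidine) defines relative dose intensity as "100 \times [\text{total actual dose}] / [\text{total assigned dose" (closing brackets omitted). The denominator, total assigned dose in mg/m², "is the total dose expected if the subject had taken all doses as initially assigned". S is defined to "be the study day of the last date that the subject is exposed to azacitidine", and D to "be the assigned dose level of 75 in" mg/m². The formula for the total assigned dose is "D \times 7 \times \lfloor S/28 \rfloor + \min[(S - 28 \times \lfloor S/28 \rfloor)/7, 1", after which only the square bracket of the minimum closes. No bracket extends D × 7 over the second term.

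SAP section 4.1.5 gives the schedule: azacitidine is administered "for 7 days during the first 9-day or less period" of each 28-day cycle.

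Section 6.4 has these exposure variables summarized descriptively in the safety population, and SAP Appendix A lists the output as Table 3.1. For contrast, the nivolumab formula in section 6.4.4 puts both of its terms inside one bracket and multiplies the whole by D.

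**The concern.** Under ordinary operator precedence the first term is a dose in mg/m² and the second is a number between 0 and 1 with no unit. They cannot be added. The second term is evidently the fraction of the last course that should have been given by day S, and it needs the factor D × 7 to become a dose. Without that factor the formula contradicts the definition in words that stands beside it.

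The error is not confined to unusual subjects. Dosing falls in the first 7 to 9 days of a cycle, so the last exposure day nearly always lies in a partial block and the last course is nearly always lost from the denominator. The distortion is greatest for those who stop early.

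The stake is the reading of azacitidine delivery in TG D and D1. Section 6.5 defines compliance for INCB059872 only, so RDI is the one planned figure for how much of the intended azacitidine dose was given. Protocol section 1.6.4 names myelosuppression as azacitidine's main DLT, and section 1.6.2 reports thrombocytopenia DLTs with INCB059872. How far the azacitidine dose could be maintained therefore bears on the tolerability of the combination.

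**Working it through.** The SAP gives no worked RDI, so there is no stated figure to reproduce. The check evaluates the printed formula and compares it with the SAP's own definition.

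**Inputs**
- D = 75 mg/m² (SAP 6.4.3).
- 7 doses per 28-day cycle (SAP 4.1.5), so a full course is 75 × 7 = 525 mg/m².
- S = study day of last azacitidine exposure (SAP 6.4.3). With undelayed cycles and the last dose on Day 7 of cycle k, S = 28(k − 1) + 7.

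**Formulas.** Write f = min[(S − 28 × floor(S/28))/7, 1].
- Printed: assigned = 525 × floor(S/28) + f
- Bracketed: assigned = 525 × {floor(S/28) + f}
- Shortfall of the printed form: (525 − 1) × f = 524f mg/m²

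The shortfall is zero only when f = 0, that is, when S is an exact multiple of 28. On an undelayed schedule that is not an azacitidine day.

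**Fully dosed subject, last dose on Day 7 of cycle k**

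| k | S | Actual (mg/m²) | Assigned, printed | RDI, printed | Assigned, bracketed | RDI, bracketed |
|---|---|---|---|---|---|---|
| 1 | 7 | 525 | 0 + 1 = 1 | 52,500% | 525 | 100% |
| 2 | 35 | 1050 | 525 + 1 = 526 | 199.6% | 1050 | 100% |
| 3 | 63 | 1575 | 1050 + 1 = 1051 | 149.9% | 1575 | 100% |
| 6 | 147 | 3150 | 2625 + 1 = 2626 | 120.0% | 3150 | 100% |
| 12 | 315 | 6300 | 5775 + 1 = 5776 | 109.1% | 6300 | 100% |

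For a course spread over nine days (S = 9, 37, 65), f is still 1 and the results for k = 1, 2 and 3 are the same. For k of 2 or more the printed RDI is close to k/(k − 1). A subject who stops after three doses (S = 3) has f = 3/7 = 0.4286, so the printed RDI is 225/0.4286 = 52,500%; the bracketed form gives 225/225 = 100%.

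**Half of every dose for two cycles.** Actual = 14 × 37.5 = 525 mg/m². Printed RDI = 525/526 = 99.8%. Bracketed RDI = 525/1050 = 50%.

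**Effect on a mean.** In a group of 30, the planned size of TG D1, one fully dosed subject who stops after cycle 1 shifts the mean RDI by (52,500 − 100)/30, about 1,747 percentage points.

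**Comparison with nivolumab (D = 3 mg/kg).** The bracketed formula in section 6.4.4 gives 3, 6, 9 and 12 mg/kg at S = 1, 15, 29 and 43, as one, two, three and four doses require.

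**The case against.** Five points can be made on the other side.

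- **A bracket may have been lost when the equation was converted to text.** This cannot be ruled out. It is not likely: the floor and minimum brackets in the same formula survived, as did the outer bracket in the neighboring nivolumab formula. A check against the source SAP settles it.
- **The intent is clear from the definition, and a programmer would notice.** A value of 52,500% would be noticed. Values of 109% or 120%, or 99.8% for a halved dose, might not be. A prespecified derivation should not depend on someone correcting it silently.
- **RDI has little weight in this trial.** This stands. The SAP does not describe RDI as a test of whether azacitidine can be delivered; that role is inferred. RDI enters no endpoint, DLT rule or futility rule, and all analyses are exploratory. Low delivery could also show up in the cycle count, in the counts of subjects with reductions or interruptions, and in the adverse-event tables for azacitidine reduction, interruption and discontinuation.
- **Cycles may drift from 28 days.** SAP 4.1.5 allows this, and Day 1 is the first dose of any study drug, so S need not be 7, 35 or 63. Drift changes the size of the error. Its direction stays the same, because the printed denominator is too small at every S that is not a multiple of 28.
- **The bracketed form is not exact for a weekend break.** With dosing on Days 1 to 5, 8 and 9, a subject who stops after Day 8 has had all 6 doses due (450 mg/m²), but the formula assigns 525, for an RDI of 85.7%. This is a small approximation and no reason to keep the printed form.

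**Conclusion.** The formula is wrong as written. It mixes units and does not yield the quantity the SAP defines. For a fully dosed subject whose last course is complete, the denominator is 524 mg/m² too small. RDI then reads 52,500% after one cycle, 199.6% after two, 149.9% after three, 120.0% after six and 109.1% after twelve, where 100% is correct.

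These figures assume undelayed 28-day cycles, azacitidine starting on Day 1 and S equal to the last dosing day. The conclusion also assumes that the printed equation matches the source SAP.

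The damage is confined to the Group D azacitidine RDI in Table 3.1. There, means would be uninterpretable, medians would be biased upward, and some under-dosing would read as full delivery. The point should be corrected before the table is programmed; it does not threaten the trial's conclusions on safety or response.

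**What to change.** After checking the source SAP, replace the formula in section 6.4.3 with:

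total assigned dose (mg/m²) = D × 7 × { floor(S/28) + min[(S − 28 × floor(S/28))/7, 1] }

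Make the same change in the derivation program and record it in SAP section 11.2. A useful program test is that a fully dosed subject returns 100% at S = 7, 9, 35, 37, 63 and 65. One sentence could note that the last-cycle term is approximate when a course is interrupted by a weekend break.

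The cost is one pair of brackets in the SAP and one line of code. No data collection, dose or clinical rule is affected.

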#### 6.4.4. Exposure for Nivolumab

- **Number of cycles:** Number of cycles with a nonzero dose of nivolumab.
- **Relative dose intensity of nivolumab (%):**  $100 \times [\text{total actual dose}] / [\text{total assigned dose}]$ .

Total actual dose ( $\text{mg}/\text{kg}$ ) administered is the sum of the weight-adjusted cumulative dose of nivolumab that has been administered to the subject.

Total assigned dose ( $\text{mg}/\text{kg}$ ) is the total dose expected if the subject had taken all doses as initially assigned. Let  $S$  be the study day of the last date that the subject is exposed to nivolumab. Let  $D$  be the assigned dose level of 3 in  $\text{mg}/\text{kg}$ . The total assigned dose is defined as

$$\text{total assigned dose } (\text{mg}/\text{kg}) = D \times (\lceil S/28 \rceil + \lceil (S - 14) / 28 \rceil),$$

where  $\lceil . \rceil$  assigns the smallest integer not less than the argument.

- **Nivolumab dose modifications:** Number of subjects who had nivolumab dose reduction and interruption will be summarized.

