**Table 7: Schedule of Assessments (Continued)**

Procedure	Protocol Section	Screening	Treatment						EOT	Follow-Up		Notes
			Cycle 1			Cycles 2+				Safety	Disease Status	
		Days -28 to -1	Day 1	Day 8 (± 2 Days)	Day 15 (± 2 Days)	Day 22 (± 2 Days)	Day 1 (± 2 Day)	Day 15 (± 2 Days)		30 Days (+5 Days)	Every 8-9 Wks	
Administer INCB059872 at site	N/A		X	X*	X*	X*	X**					* Subjects should not take drug at home but must bring medication; they will take their dose after initial PK blood draw. NOTE: Drug is not given on Day 8, but if on a dosing day, subject should follow rules above. ** TG B1 subjects for food-effect study.
Assess compliance	5.3			X	X	X	X	X	X			
Administer ATRA at site			X*	X*	X*	X*						* 45 mg/m  per day administered as 2 evenly divided doses; AM dose only in the clinic.
Administer azacitidine at site			X*	X*	X*	X*	X*					* 75 mg/m  SC or IV for 7 days during the first 9-day or less period (ie, a 2-day break allowed on weekend, if needed) of each 28-day treatment cycle.
Administer nivolumab at site			X*		X*		X*	X*				* 3 mg/kg Q2W.
Distribute reminders	7.10.1	X	X	X	X	X	X	X				

CT = computed tomography; [REDACTED]; MRI = magnetic resonance imaging; [REDACTED]; [REDACTED]

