## **6.2. Treatment**

The treatment period begins on the day the subject receives the first dose of study drug (Cycle 1 Day 1) through the point at which the investigator determines the subject will be permanently discontinued from study drug. Cycle 1 Day 1 must be no more than 28 days after the subject has signed the ICF and no more than 3 days after the date of registration. Dates for subsequent study visits will be determined based on this day and should occur within the specified visit windows noted in [Table 7](#) and [Table 8](#) of the scheduled date unless delayed for safety reasons. At Cycle 1 Day 1, results from screening visit evaluations should be reviewed to determine whether the subject continues to meet the eligibility requirements, as specified in Section 3.

Note: Day 15 visits beyond Cycle 4 may be optional (except for subjects in TG E/E1) per subject overall status and approval by the sponsor medical monitor.

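### SAP 6.4.4 omits a final nivolumab dose given 1 or 2 days early within the visit window, so a fully dosed subject with k ≥ 2 doses is reported at k/(k − 1) instead of 100%

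*SAP*

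**What the plan says.** SAP 6.4.4 reports relative dose intensity for nivolumab as 100 × total actual dose / total assigned dose. The assigned dose "is the total dose expected if the subject had taken all doses as initially assigned". To compute it, the section lets S "be the study day of the last date that the subject is exposed to nivolumab" and D "be the assigned dose level of 3 in" mg/kg, and sets the assigned dose to D × (⌈S/28⌉ + ⌈(S − 14)/28⌉), where the bracket "assigns the smallest integer not less than the argument". S is an actual calendar day under SAP 4.1.2, not a nominal visit.

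SAP 4.1.5 places nivolumab on "Day 1 and Day 15 of each 28-day treatment cycle". The same section takes the actual Day 1 of a later cycle from the eCRF and accepts that cycles may depart from 28 days.

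In Protocol Table 7 the row "Administer nivolumab at site" is marked at Cycle 1 Day 1, Cycle 1 Day 15, and Days 1 and 15 of later cycles. All of these except Cycle 1 Day 1 carry a window of plus or minus 2 days. Protocol 6.2 anchors the visits to Cycle 1 Day 1: "Dates for subsequent study visits will be determined based on this day and should occur within the specified visit windows noted in" Tables 7 and 8. No separate window or minimum interval is given for nivolumab, and SAP 6.4.4 has no window allowance, nominal-visit rule or cap.

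**The concern.** The denominator follows a strict 14-day calendar, while the numerator takes whatever was given inside a visit window. A last dose that is early but compliant is therefore counted as given and not as assigned. By the SAP's own definition, a subject who received every assigned dose should read 100%, and this subject reads more.

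The error goes only upward, so it can offset real shortfalls in the Group E average, for example from nivolumab withheld for immune-related events. It is largest in subjects who stop after 2 or 3 doses, where tolerability of the combination is most in question. Group E is also summarized by dose level (SAP 5.2), and an escalation level may hold only 3 to 6 subjects (SAP 3.3). In a cell of 3, one value of 200% beside two of 100% gives a mean of (200 + 100 + 100)/3 = 133%.

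**Working it through.** **Inputs.** D = 3 mg/kg, S and the formula (SAP 6.4.4); dosing on Days 1 and 15 of 28-day cycles (SAP 4.1.5), so dose k is nominally on day 14(k − 1) + 1; window of ±2 days (Protocol Table 7), anchored to Cycle 1 Day 1 (Protocol 6.2). The subject misses no dose, so the actual dose is 3k mg/kg.

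**Nominal days.** The SAP states no numerical result here, so the formula is first tried on the planned days. S = 1, 15, 29, 43 gives 1, 2, 3, 4 doses, or 3, 6, 9, 12 mg/kg, and 100% each time. The formula is exact on schedule.

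**Last dose 1 or 2 days early.** For dose 2:
- S = 13: ⌈13/28⌉ + ⌈−1/28⌉ = 1 + 0 = 1 dose.
- S = 14: ⌈14/28⌉ + ⌈0/28⌉ = 1 + 0 = 1 dose.
- Assigned 3 mg/kg, given 6 mg/kg: 6/3 = 200%.

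For dose 3, S = 27 or 28 gives 1 + 1 = 2 doses, and 9/6 = 150%. In general the formula returns k − 1 doses, and the result is k/(k − 1):

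| Last dose k | S if early | Assigned (mg/kg) | Given (mg/kg) | Reported |
|---|---|---|---|---|
| 2 | 13, 14 | 3 | 6 | 200% |
| 3 | 27, 28 | 6 | 9 | 150% |
| 4 | 41, 42 | 9 | 12 | 133.3% |
| 6 | 69, 70 | 15 | 18 | 120% |
| 7 | 83, 84 | 18 | 21 | 116.7% |
| 9 | 111, 112 | 24 | 27 | 112.5% |
| 14 | 181, 182 | 39 | 42 | 107.7% |

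**Unaffected cases.** A last dose on time or 1 to 2 days late gives 100% for every k from 1 to 14. An early dose followed by an on-time last dose causes no error, because only the last dose sets S.

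**Group effect.** If a fraction p of subjects stopping after k doses had an early last dose, their mean rises by p/(k − 1). The documents give no value for p. With p = 20% (assumed), the rise is 20 points at k = 2 and 20%/8 = 2.5 points at k = 9. Over all p from 0 to 100%, the rise runs from 0 to 100 points at k = 2 and from 0 to 12.5 points at k = 9.

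**Day-based replacement, D × (1 + ⌊(S + 1)/14⌋).**
- S = 13 to 17 gives 2 doses and S = 27 to 31 gives 3. The equivalent form with S replaced by S + 2 in the SAP formula gives 100% at every offset from −2 to +2 days for doses 1 to 14.
- Early drift: if Cycle 2 Day 1 falls on Day 27 and its Day 15 visit falls 2 days early, dose 4 is on Day 39. The count is 1 + ⌊40/14⌋ = 3, and the result is still 4/3 = 133%.
- Late second dose on Day 27 or 28 with no third dose: the count is 1 + ⌊28/14⌋ or 1 + ⌊29/14⌋ = 3, so the result is 2/3 = 67%, where the SAP formula gives 2/2 = 100%.

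**The case against.** The strongest defence is that the formula is not wrong but literal: by Day 13 the assigned calendar calls for one dose, and what is missing is a window convention. That describes the cause correctly. It does not rescue the result, because the numerator follows the window and the denominator does not. Nor is 200% a fair measure of faster dosing: shortening one interval from 14 to 12 days raises the dosing rate by 14/12, or 117%.

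The objections to the size of the problem stand, and three stronger readings should be set aside.

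- A reader might infer that any fully dosed subject with an early last dose reads 120% to 200%. That range holds only when the last dose is the 2nd to the 6th. The Protocol expects participation of about 6 months. Assuming about 1 month each for screening and follow-up leaves about 4 months of treatment, roughly 9 doses, where the figure is 112.5%.
- A reader might infer that the SAP has no other view of whether nivolumab was delivered. It also counts subjects with nivolumab reductions and interruptions (6.4.4), tabulates adverse events leading to reduction, interruption and discontinuation (Tables 3.2.21, 3.2.23, 3.2.25), and lists drug administration (Listing 2.7.1).
- A reader might infer an effect on safety or dosing decisions. Relative dose intensity enters no endpoint, futility rule or dose-limiting toxicity decision. SAP 5.1 includes the median and maximum in its summaries, so an isolated 200% would be visible.

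**Conclusion.** The formula is wrong as written, for a narrow set of subjects: those in TG E/E1 with at least two nivolumab doses whose last dose was 1 or 2 days early. Each reads k/(k − 1) instead of 100%. This rests on visit windows anchored to Cycle 1 Day 1, as Protocol 6.2 states, and on no other dose having been missed. How many subjects are affected cannot be determined from the documents.

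The consequence is limited to the Group E part of the descriptive exposure summary (SAP Table 3.1). It is a minor correction, worth making because it is cheap and because the output would show an impossible value for a compliant subject.

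**What to change.** Define the total assigned nivolumab dose as D × the number of planned Day 1 and Day 15 administrations up to and including the nominal eCRF visit of the last dose, and keep omitted planned visits in the denominator. This agrees with SAP 4.1.5, which already takes the cycle Day 1 from the eCRF. A second dose on Day 13 recorded as Cycle 1 Day 15 gives 6/6 = 100%. The Day 39 dose recorded as Cycle 2 Day 15 gives 12/12 = 100%. A subject dosed at Cycle 1 Day 1 and Cycle 2 Day 1, with Day 15 omitted, gives 6/9 = 67%. The SAP should also say to which visit a substantially delayed dose is assigned.

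If a formula in S is preferred, use D × (1 + ⌊(S + 1)/14⌋) and state its limits: it does not handle cycles that drift early by more than 2 days in total, and it counts a second dose delayed to Day 27 or 28 as one missed dose (67%). No formula in S alone can tell an early third dose from a late second one.

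The cost is one definition in the SAP and the matching program. No new data are needed if each infusion is already recorded against a cycle and visit, which is assumed here.
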